# 2.1.3 Exploratory Objectives

- Longitudinal assessment of genomic minimal residual disease (MRD) to determine the kinetics of response and the association with relapse-free survival.
- Explore the impact of CD33 variants, and the degree of CD33 expression on leukemic blasts, on the response rates and relapse-free survival.
- Explore the relationship between leukemic blast BH3 profiling and response rates.

• Explore the relationship between leukemic blast expression of anti-apoptosis proteins (BCL-2, BCL-XL and MCL-1) and response rates.

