# 2.2.3 Correlative/ Exploratory Endpoints

- Genomic MRD with droplet digital PCR (ddPCR) will be measured to determine kinetics of response and the association with relapse-free survival at the end of cycles 1 and 2, at 6 months and 12 months, and if there is evidence of relapse. (Sub-PI is [name] [see ref. 33].)
- CD33 DNA polymorphisms will be measured at presentation and at relapse.
- Leukemic blast CD33 expression will be measured at presentation and at relapse.
- "BH3 profiling" of AML blasts will be performed at presentation and at relapse.
- BCL-2, BCL-XL, and MCL-1 protein levels in PB or BM blasts will be measured at presentation and after 6 days (i.e., Cycle 1 Day +3) of Venetoclax therapy

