# 5.3 Dose Cohorts

# 5.4 Induction (Cycle 1) and Consolidation (Cycle 2):

Cycle 1: Gemtuzumab Ozogamicin (GO) 3 mg/m^2 IV infusion (up to one 4.5 mg vial) will be given on days +1, +4, and +7 in combination with daily oral administration of Venetoclax during Induction. Based on previous studies, Venetoclax dose will start at 200 mg daily with dose escalation planned over 3 cohorts to identify the recommended phase 2 dose (RP2D). Dose cohort 3 will use the maximum dose of Venetoclax of 600 mg orally daily. Because of evidence of tumor lysis syndrome (TLS) with Venetoclax use in previous CLL studies, we will use a 3-day stepwise ramp up in cycle 1 to the target dose for all cohorts (see Table 1). Patients should expect to be hospitalized throughout Induction/Cycle 1, although medically stable patients may be discharged from the hospital under close supervision at the discretion of the treating physician. Patients do not have to be hospitalized during the first week of consolidation if the treating physician wishes to administer Gemtuzumab (C2D1 and D4) in the outpatient clinic.

Day	Cohort 1 (mg)	Cohort 2 (mg)	Cohort 3 (mg)
-2	50	50	100
-1	100	100	200
0	100	200	400
1–28	200	400	600

Table 1. Venetoclax Ramp-up schedule

Clinical and hematological responses will be assessed after the end of both the induction and consolidation cycles. Bone marrow assessment will occur on day 28 regardless of absolute neutrophil count (ANC) or platelet recovery.

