- **8.1.4** BCL-2 Family Protein Analysis prior to, and after Venetoclax exposure may reveal adaptive changes in anti-apoptotic protein expression. Leukocytes isolated from pretreatment and Day+3 (C1D3) peripheral blood will be analyzed by semi-quantitative Western blot analysis for BCL-2, BCL-XL and MCL-1 expression. If sufficient samples are available then PBMNC samples from pretreatment and Day+3 will also be permeabilized, incubated with fluorescent antibodies to BCL-2, BCL-XL and MCL-1, and expression measured by flow cytometry. Analysis will also be performed on relapse samples (if this occurs). These experiments will be performed at the University of Illinois in the laboratory of [name].

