# **8.2.3** Peripheral blood:

Peripheral blood samples will be collected prior to treatment, at Cycle 1 Day  $+3 (\pm 1 \text{ day})$ , at the end of the induction cycle (Cycle 1 Day  $28 \pm 3$  days), at the end of the consolidation cycle (Cycle 2 Day  $28 \pm 3$  days), at pre-treatment cycle 7 day 1 (i.e. ~6 months after initial treatment) ( $\pm 14$  days), at pre-treatment cycle 13 day 1 (i.e. ~12 months after initial treatment) ( $\pm 14$  days), and at any time of suspected relapse. Correlative peripheral blood samples will preferentially be obtained during clinically indicated peripheral blood draws. Plasma will be isolated and frozen, and leukocytes will be isolated by Ficoll gradient centrifugation and cryopreserved for use in the correlative studies described. See CLM for collection, labeling, processing, and shipping instructions.

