# 8.3 Storage of Biospecimens

# 8.3.1 Specimen Processing and Storage:

Buccal swabs will be stored at  $-20^{\circ}$  until DNA extraction. Plasma will be isolated from peripheral blood tubes and stored in aliquots at  $-80^{\circ}$ . Bone marrow aspirates and peripheral blood samples will undergo Ficoll gradient centrifugation and mononuclear cells with be aliquoted and cryopreserved in liquid nitrogen. These samples will be stored in the central lab for use in the correlative studies outlined in this protocol as well as for future research.

Please refer to the Correlative Laboratory Manual (CLM) for all sample collection, processing, labeling, and shipping instructions.

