# 12.6.2 Analysis Plans for Secondary Objectives

Descriptive characteristics of all adverse effects of GO in combination with Venetoclax (using CTCAE v5 criteria) will be reported; and the efficacy of the combination in achieving ORR (includes CR/CRi) and anti-leukemic activity (includes CR/CRi/PR), as defined by the revised IWG criteria), RFS, EFS, and OS in subjects. The effects of therapy on quality of life, fatigue, and physical function at D0 (trial entry) and the end of every other month for 1 year (see section 8.1) will be reported and analyzed using generalized linear modeling.

All time-to-event outcomes (e.g. survival) will be calculated using Kaplan Meier methods and exploratory log-rank tests will be used to compare treatment effect between groups based on genomic MRD, CD33 DNA polymorphisms, BH3 profiling and anti-apoptosis protein levels in PB MBCs at presentation and after 1 week of Venetoclax.

*Sample size permitting:* Hazard ratios (HR) and 95% CIs will be produced. Time-to-event outcomes with a competing or semi-competing risk (e.g. CIR) will be analyzed using cumulative incidence curves and exploratory comparisons between arms will be made using Grey's test. Rate ratios and 95% CIs will be presented. Chi squared tests will be used to assess the treatment effect between cohorts for all categorical variables and t-tests or Mann Whitney tests will be applied for continuous measures as appropriate.

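### The BCL-2, BCL-XL and MCL-1 endpoint is defined in leukemic blasts, but the only assured assay reads unsorted blood mononuclear cells, so the Day +3 value may mix blast expression with blast fraction

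*Combined protocol and SAP*

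**What the plan says.** **Objective (2.1.3).** "Explore the relationship between leukemic blast expression of anti-apoptosis proteins (BCL-2, BCL-XL and MCL-1) and response rates".

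**Endpoint (2.2.3, repeated in 12.2.3).** "BCL-2, BCL-XL, and MCL-1 protein levels in PB or BM blasts will be measured at presentation and after 6 days" of venetoclax. The same sentence equates that time with Cycle 1 Day +3.

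**Assay (8.1.4).** "Leukocytes isolated from pretreatment and Day+3 (C1D3) peripheral blood will be analyzed by semi-quantitative Western blot analysis for BCL-2, BCL-XL and MCL-1 expression". Flow cytometry is conditional: "If sufficient samples are available then PBMNC samples from pretreatment and Day+3 will also be permeabilized". No blast gate is stated for it. The section presents the comparison as before and after venetoclax, and says that it may show adaptation of these proteins.

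**Sample handling.** Section 8.2.3: "leukocytes will be isolated by Ficoll gradient centrifugation and cryopreserved for use in the correlative studies described". Section 8.3.1: "Bone marrow aspirates and peripheral blood samples will undergo Ficoll gradient centrifugation and mononuclear cells with be aliquoted".

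**Analysis (12.6.2).** The grouping factors for exploratory log-rank tests include "anti-apoptosis protein levels in PB MBCs at presentation and after 1 week of Venetoclax". I read the printed abbreviation as mononuclear cells.

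**Timing.** In cycle 1, GO "will be given on days +1, +4, and +7 in combination with daily oral administration of Venetoclax during Induction" (5.4). The on-treatment blood draw is Day +3 with a window of one day either side (section 7 footnotes and 8.2.3). Section 8.2.2 lists no marrow sample at that time.

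**The concern.** A Western blot of a lysate averages over whatever cells are loaded. Ficoll separation reduces granulocytes but leaves lymphocytes and monocytes beside the blasts. The blot therefore reports a weighted mean in which the weight is the blast share of the sample, and the endpoint asks for one component of that mean.

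The weight may move between the two draws. GO binds CD33, which section 1.2.1 places on more than 90% of AML blast cells, and venetoclax has started as well. The regimen is meant to remove the cells whose protein is being tracked. A patient who clears blasts early could show a changed bulk signal with no change in any blast. If such patients are also the responders, protein level and outcome would appear linked for that reason alone.

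Resistance through this protein family is central to the rationale in sections 1.2.1, 1.3 and 1.3.1, so the result is likely to be read mechanistically. If blast percentages are not tied to the samples, the two explanations cannot be told apart afterwards.

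**Working it through.** The documents give no target, effect size or power for this endpoint, so there is no figure of theirs to reproduce.

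**1. Timing (5.4, Table 1, section 7).** Venetoclax days up to the draw are -2, -1, 0, 1, 2 and 3, which is 6 and agrees with 2.2.3. The window (Day 2 to Day 4) gives 5 to 7. The first GO dose is on Day 1, so the draw falls 3 - 1 = 2 days later, or 1 to 3 days with the window. Day 4 is also the day of the second GO dose. The one week in 12.6.2 is reached only at the late edge of the window.

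**2. Mixture.** Let f be the blast share of the mononuclear cells and r the protein per blast divided by the protein per non-blast. Then

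bulk signal = f × r + (1 - f).

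Per-cell levels are held fixed, so any shift comes from composition alone. All values of f and r are assumptions.

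| r | f = 0.6 | f = 0.1 | Change, 60% to 10% | f = 0.5 | Change, 60% to 50% |
|---|---|---|---|---|---|
| 1/3 | 0.600 | 0.933 | +56% | 0.667 | +11% |
| 1/2 | 0.70 | 0.95 | +36% | 0.75 | +7% |
| 1 | 1.0 | 1.0 | 0% | 1.0 | 0% |
| 2 | 1.6 | 1.1 | -31% | 1.5 | -6% |
| 3 | 2.2 | 1.2 | -45% | 2.0 | -9% |

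**3. Pretreatment level.** On-treatment clearing cannot affect it, but it still depends on f. Two patients with identical blasts and shares of 60% and 30% differ by 1.6 / 1.3 = 1.23 at r = 2, and by 2.2 / 1.6 = 1.375 at r = 3.

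**4. False link with response.** This simulation used 5,000 trials per setting and a two-sided Mann-Whitney test at 0.05 of log(Day +3 / baseline) in responders against non-responders, with no true change per blast. Total sample size is 15 or 24 (Synopsis range). The 33% response rate is borrowed from the earlier fractionated-GO trial in 1.2.1. Assumed inputs are a mean pretreatment blast share of 60%, a log-scale assay SD of 0.3, and the share of blasts surviving to Day +3.

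| Survival of blasts, responders vs non-responders | r | N = 15 | N = 24 |
|---|---|---|---|
| 20% vs 70% | 1/2 | 10% | 19% |
| 20% vs 70% | 1 | 4% | 5% |
| 20% vs 70% | 2 | 14% | 25% |
| 20% vs 70% | 3 | 29% | 50% |
| 40% vs 70% | 2 | 6% | 9% |
| 40% vs 70% | 3 | 8% | 15% |
| 50% vs 50% | 1/2 to 5 | 3-4% | 4-5% |

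A blast-specific readout gave 3% to 5% throughout. The plan does not specify this test. It stands in for any comparison of the on-treatment shift with outcome.

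**The case against.** The strongest case against is that the mechanism is conditional and the numbers are assumed. A reader might infer that clearing blasts shifts the result by itself. It does not: at r = 1 nothing moves, and with equal clearing in both groups the false-positive rate stays nominal. Nor do the documents show that circulating blasts are falling by Day +3. That is plausible for this regimen, but no kinetics are given. All of this stands, and it limits the claim to what can happen.

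Other stronger readings also fail:

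- The blot does not take all blood leukocytes. The Ficoll step makes the sample a mononuclear fraction, which narrows the mixing without ending it.
- Section 12.6.2 makes no claim about adaptation or change. It lists levels at two times as exploratory grouping factors. Only 8.1.4 speaks of adaptive change, and it says may.
- The timing conflict is between two statements, not three: 6 days is equated with Day +3, and only one week differs.
- The false-link argument does not reach the pretreatment level, and the objective in 2.1.3 could be met with that level alone.

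The Correlative Laboratory Manual and the published assay methods cited in 8.1.4 were not available and might specify gating or purity. The protocol cites the manual for collection, processing, labeling and shipping rather than analysis, so the endpoint definition still needs the statement.

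Making flow mandatory would not be a clean cure. It is conditional because sample may run short, and the samples with too few blasts to gate would come from the fastest-clearing patients. Mixing would be exchanged for missing data related to outcome.

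**Conclusion.** The point holds in a limited form. As written, the assured assay does not measure the endpoint as defined: blasts are named in 2.1.3, 2.2.3 and 12.2.3, while 8.1.4 and 12.6.2 use unsorted mononuclear cells, and nothing links the two. The Day +3 level, and any change from baseline, mixes blast expression with blast fraction if r differs from 1. A false link with response or survival further requires early clearing to differ by outcome.

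Size and direction are unknown. Under the assumptions shown, the composition effect for a clearing patient runs from none at r = 1 to -31% to -45% at r = 2 to 3, or +36% to +56% at the inverse ratios.

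Separately, and without any assumption, a change at Day +3 cannot be attributed to venetoclax alone, because the draw follows the Day 1 GO dose throughout its window.

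Priority is low. The endpoint is exploratory, and DLT assessment, the MTD and the secondary endpoints are unaffected.

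**What to change.** 1. **8.1.4, Western blot.** Record the blast percentage for each sample from the same-day CBC with differential, and use it in the analysis of the blot. Because the blot sample is mononuclear, blasts / (blasts + lymphocytes + monocytes) is the closer approximation to f. This makes the mixing visible and partly adjustable. It does not turn a bulk blot into a blast measurement.
2. **8.1.4, flow cytometry.** Where it is run, gate on blasts and treat the gated value as the preferred readout of the endpoint. Report how many samples are unevaluable, because low-blast samples come from fast-clearing patients.
3. **Attribution.** Describe the Day +3 result as the effect of venetoclax plus GO.
4. **Wording.** Align cell population (blasts or mononuclear cells) and timing (6 days/C1D3 or one week) across 2.2.3, 8.1.4, 12.2.3 and 12.6.2.

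I would neither require flow for every sample, for the reason given above, nor add a tube on C1D1 before GO. That tube would be a new collection and would reflect little beyond the ramp-up doses.

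**Cost.** Slightly more analysis work and some unevaluable low-blast samples. The section 7 footnotes already call for a daily CBC while patients are in hospital. For a patient discharged before Day +3, the differential would have to accompany the correlative draw.

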# 8.1.5. BH3 profiling predicts response to therapy.

Thawed BM samples from pretreatment and, potentially, relapse samples will be permeabilized, incubated with various BH3 peptides and subsequently mitochondrial cytochrome C release measured by flow cytometry analyses. These experiments will be performed at the University of Illinois in the laboratory of [name].

**8.1.6** Quality of life, fatigue, and physical function will be assessed at baseline and every other month for one year to measure the effects of therapy. Quality of life (QOL) will be assessed using the European Organization for the Research and Treatment of Cancer 30 item questionnaire (EORTC QLQ-C30). The questionnaire is scored from 0 to 100, higher scores positively correlate with a better QOL. The Functional Assessment of Cancer Therapy Fatigue (FACT-Fatigue) questionnaire consists of 13 items with scores ranging from 0 to 52, higher scores positively

correlate with less fatigue. Objective physical measures will consist of a two-minute walk test, and timed chair stands. See Appendix V for sample questionnaires.

# 8.2 Source and Timing of Biospecimen Collections

# 8.2.1 Buccal swab:

Patients will have buccal mucosal cells collected prior to treatment using two buccal swabs to provide germline DNA. See Correlative Laboratory Manual (CLM) for collection, labeling, processing, and shipping instructions.

# 8.2.2 Bone marrow aspirate:

Bone marrow aspirate material will be collected will be collected prior to treatment, at the end of the induction cycle (Cycle 1 Day  $28 \pm 3$  days), at the end of the consolidation cycle (Cycle 2 Day  $28 \pm 3$  days), at pre-treatment cycle 7 day 1 (i.e. ~6 months after initial treatment) ( $\pm$  14 days), at pre-treatment cycle 13 day 1 (i.e. ~12 months after initial treatment) ( $\pm$  14 days), and at any time of suspected relapse. Leukocytes from the bone marrow aspirate will be isolated by Ficoll gradient centrifugation and cryopreserved for use in the correlative studies described. See CLM for collection, labeling, processing, and shipping instructions.

# **8.2.3** Peripheral blood:

Peripheral blood samples will be collected prior to treatment, at Cycle 1 Day  $+3 (\pm 1 \text{ day})$ , at the end of the induction cycle (Cycle 1 Day  $28 \pm 3$  days), at the end of the consolidation cycle (Cycle 2 Day  $28 \pm 3$  days), at pre-treatment cycle 7 day 1 (i.e. ~6 months after initial treatment) ( $\pm 14$  days), at pre-treatment cycle 13 day 1 (i.e. ~12 months after initial treatment) ( $\pm 14$  days), and at any time of suspected relapse. Correlative peripheral blood samples will preferentially be obtained during clinically indicated peripheral blood draws. Plasma will be isolated and frozen, and leukocytes will be isolated by Ficoll gradient centrifugation and cryopreserved for use in the correlative studies described. See CLM for collection, labeling, processing, and shipping instructions.

# 8.3 Storage of Biospecimens

# 8.3.1 Specimen Processing and Storage:

Buccal swabs will be stored at  $-20^{\circ}$  until DNA extraction. Plasma will be isolated from peripheral blood tubes and stored in aliquots at  $-80^{\circ}$ . Bone marrow aspirates and peripheral blood samples will undergo Ficoll gradient centrifugation and mononuclear cells with be aliquoted and cryopreserved in liquid nitrogen. These samples will be stored in the central lab for use in the correlative studies outlined in this protocol as well as for future research.

Please refer to the Correlative Laboratory Manual (CLM) for all sample collection, processing, labeling, and shipping instructions.

# 8.4 Banking of Leftover Biospecimens

Subject consent will be obtained to bank any leftover samples collected for study-specific correlative research. Hoosier Cancer Research Network (HCRN), as Administrative Headquarters for the Big Ten CRC, will manage the banked samples. Samples will be banked

indefinitely in the Hoosier Cancer Research Network Biorepository and used for future unspecified cancer-related research.

#### 8.5 Banking Samples for Future Unspecified Research

Subject consent will be obtained to collect additional blood samples for future unspecified Big Ten Cancer Research Consortium studies. HCRN will manage the banked samples. Samples will be banked indefinitely in the HCRN Biorepository.

#### 8.6 Confidentiality of Biospecimens

Samples will be identified by a subject's study number assigned at the time of registration to the trial. Any material issued to collaborating researchers will be anonymized and only identified by the subject's study number.

# 9. CRITERIA FOR DISEASE EVALUATION

#### 9.1 Definitions of Response to Treatment in AML

Disease will be assessed according to the International Working Group Criteria.

Category	Definition					
Treatment Success categories						
Complete remission (CR)	Bone marrow blasts < 5%; absence of blasts with Auer rods; absence of extramedullary disease; absolute neutrophil count > $1.0 \times 10^{9}/L$ ( $1000/\mu$ L); platelet count > $100 \times 10^{9}/L$ ( $100,000/\mu$ L); independent of red cell transfusions					
CR with incomplete recovery (CRi)	All CR criteria except for residual neutropenia $< 1.0 \times 10^{9}/L$ (1000/µL) or thrombocytopenia $< 100 \times 10^{9}/L$ (100,000/µL)					
Partial remission (PR)	All hematologic criteria of CR; decrease of bone marrow blast percentage to 5% to 25%; and decrease of pretreatment bone marrow blast percentage by at least 50%					
Treatment Failure categories						
Resistant Disease	Failure to achieve CR or CRi or failure to achieve CR, CRi, or PR; only includes patients surviving $\geq$ 7 days following completion of initial treatment, with evidence of persistent leukemia by blood and/or bone marrow examination					
Death in aplasia	Deaths occurring $\geq$ 7 days following completion of initial treatment while cytopenic; with an aplastic or hypoplastic bone marrow obtained within 7 days of death, without evidence of persistent leukemia					
Death from indeterminate cause	Deaths occurring before completion of therapy, or $< 7$ days following its completion; or deaths occurring $\ge 7$ days following completion of initial therapy with no blasts in the blood, but no bone marrow examination available					

Adapted from International Working Group Criteria

In patients with abnormal cytogenetics at diagnosis, CR (or CRi) will be delineated as above plus evidence of complete cytogenetic response (also known as CRc)—defined as a reversion to normal cytogenetics.

#### 9.2 Definitions of Survival Endpoints for AML

Overall Survival	All evaluable patients entered into trial; measured from the date of entry to the date of death from any cause; patients not known to have died at last follow- up are censored on the date they were last known to be alive				
Relapse-free Survival	Only patients achieving CR or CRi; measured from the date of achievement of a remission until the date of relapse or death from any cause; patients not known to have relapsed or died at last follow-up are censored on the date they were last examined				
Event-free Survival	All patients entered into trial; measured from the date of entry to the date of treatment failure, disease relapse, or death from any cause; patients not known to have any of these events are censored on the date they were last examined				
Adapted from European LeukemiaNet. 					

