#### 4. SUBJECT REGISTRATION

All subjects must be registered through Big Ten Cancer Research Consortium (Big Ten CRC) Administrative Headquarters'(AHQ) electronic data capture (EDC) system. A subject is considered registered when an 'On Study' date is entered into the EDC system.

Registration will occur after the patient has signed the patient consent and eligibility is confirmed, but before any treatment has been administered. To be eligible for registration to this study, the patient must meet each of the criteria listed on the eligibility checklist. A copy of the eligibility checklist will be retained at the participating center. Subjects must begin therapy within **5 business days** of registration.

Venetoclax dose levels will be assigned at registration.

If a patient signs consent and is registered to the study and is later found to be unable to begin the planned study treatment, for whatever reason, the patient will be removed from study and treated at the physician's discretion. The patient will be considered a screen/baseline failure and be replaced. Further data will not be collected if the patient has not begun study treatment at the time of removal from trial. The reason for removal from study will be clearly indicated in EDC.

If a patient begins treatment, and then treatment is discontinued for whatever reason, the patient must be followed per section 7.2.

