# 12.5 Assessment of Efficacy

All subjects with disease who received at least one dose of study drug and have had their disease reevaluated (or die beforehand), will be included in the efficacy analysis. Per the analysis plan described in section 12.8.2 for all time-to-event outcomes (e.g., survival) identified as secondary endpoints, cumulative incidence and hazard functions will be estimated as conditional survival probabilities until first meeting the defined outcome criteria for efficacy:

- ORR (CR/CRi) and anti-leukemic activity (CR/CRi/PR) after 2 cycles. See Section 9.1.
- Relapse-free and event-free survival
- Overall survival in subjects

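### Sections 9.2 and 12.5 give conflicting analysis sets for OS and EFS, and the 12.5 rule drops a never-re-evaluated patient only if that patient is alive

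*Combined protocol and SAP*

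**What the plan says.** Three statements bear on who is counted for survival.

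- **Section 9.2, OS row:** "All evaluable patients entered into trial; measured from the date of entry to the date of death from any cause". Survivors are censored when last known alive.
- **Section 9.2, EFS row:** "All patients entered into trial; measured from the date of entry to the date of treatment failure, disease relapse, or death from any cause". There is no evaluability condition. Patients without an event are censored when last examined.
- **Section 12.5:** the efficacy analysis takes subjects who "received at least one dose of study drug and have had their disease reevaluated (or die beforehand), will be included in the efficacy analysis". The outcomes listed beneath it include "Relapse-free and event-free survival" and "Overall survival in subjects".

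Evaluable is defined only for toxicity, in Section 12.4 (at least one dose of each drug). Section 12.6.3 also refers to patients evaluable for response, without a definition. Section 12.5 points to a Section 12.8.2 that does not exist; the analysis plan for these endpoints is in 12.6.2, which specifies Kaplan-Meier and names no analysis set.

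**The concern.** Kaplan-Meier estimation needs a set whose membership is settled at time zero, with patients whose outcome is not yet known censored rather than removed. The exception in 12.5 for patients who die before re-evaluation makes sense for response, where an early death is a non-response. Carried over to OS, it keeps the deaths among patients never re-evaluated and deletes the survivors, which bypasses the censoring rule that 9.2 provides for those survivors.

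The protocol foresees such patients. The first scheduled marrow is on Day 28 (5.4). Before then a living patient may be removed for transplant (5.6), go off study after a long gemtuzumab interruption (Table 6), or stop for toxicity or at their own request (6.3). Section 4 requires treated patients who stop to be followed under 7.2, and 7.2 allows follow-up by phone. Vital status can therefore be known without any disease re-evaluation.

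With the set unsettled, the OS and EFS curves could also rest on different patients, and the choice of set in an open-label trial could be made after outcomes are known.

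**Working it through.** **1. Inputs.** From the documents: N = 15 to 24 (Synopsis; 9–18 plus 6 gives 15–24); first re-evaluation at Day 28 (5.4); Kaplan-Meier (12.6.2). The documents state no OS or EFS figure, event count, or rate of leaving before re-evaluation, so there is no plan figure to reproduce. Assumed: median OS 6 months in patients who stay; 10–20% leave before re-evaluation.

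**2. Direction.** Kaplan-Meier is S(t) = ∏(1 − dᵢ/nᵢ) over death times up to t. If a death without re-evaluation is always kept, the 12.5 rule removes only censored patients. Removing one lowers nᵢ at every death time before that patient's last contact and leaves each dᵢ unchanged. Each factor stays the same or falls, so S(t) cannot rise. In simulation the 12.5 estimate never exceeded the all-treated estimate in any run.

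**3. Exact counts at Day 56.** Suppose 3 deaths before re-evaluation and 3 living leavers still followed at Day 56.

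| N | All treated | 12.5 set | Re-evaluated patients only |
|---|---|---|---|
| 24 | 21/24 = 87.5% | 18/21 = 85.7% (−1.8) | 18/18 = 100% (+12.5) |
| 15 | 12/15 = 80.0% | 9/12 = 75.0% (−5.0) | 9/9 = 100% (+20.0) |

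The last column applies only if evaluable in 9.2 is read as re-evaluated.

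**4. Simulated 6-month OS.** n = 24, 4,000 trials, exponential survival; entries are all treated / 12.5 set.

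| Leavers | Followed beyond 6 months | Lost by Day 28 |
|---|---|---|
| 10%, median 6 months | 0.500 / 0.475 | 0.503 / 0.500 |
| 20%, median 6 months | 0.500 / 0.449 | 0.500 / 0.494 |
| 10%, median 2 months | 0.463 / 0.458 | 0.494 / 0.491 |
| 20%, median 2 months | 0.426 / 0.415 | 0.489 / 0.482 |

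The fall is 0.5 to 5.1 points in the first column and 0.3 to 0.7 points in the second. A separate simulation with leavers censored at varied times over about 6 months, 5–20% leavers, median OS of 4, 6 or 11 months and N of 15 or 24 gave falls of about 0.6 to 3.4 points.

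**5. Precision.** At n = 24 and S = 0.50, the standard error is √(0.5 × 0.5 / 24) = 0.102, so a 95% interval is about ±20 points.

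**The case against.** The strongest reply is that few patients would meet the conditions for a sizeable shift. Section 12.5 asks only that disease be re-evaluated; it names neither Day 28 nor a marrow. Section 7.2 follows leavers for progression every 2 months for 6 months, the study calendar lists an exam and blood count in long-term follow-up, and 9.1 lets persistent leukemia be shown in blood. A leaver followed past 6 months would usually have been re-evaluated, and for patients lost by Day 28 the shift is at most 0.7 points. This stands: it limits the size. It does not settle which set governs or remove the outcome-dependent condition.

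A reader might go further and infer four things.

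- **That the plan biases OS in either direction, by as much as 8 points.** With 20% poor-prognosis leavers, 0.415 on the 12.5 set compares with 0.50 if leavers are dropped altogether. That is a gap between two rival readings, not an error against all treated patients. An upward bias needs evaluable in 9.2 to mean re-evaluated only, or to mean the 12.4 toxicity set, which would lose a death during the venetoclax-only ramp-up. The text permits these readings but does not state them; 12.4 is expressly about toxicity, and 12.5 keeps early deaths.
- **That the downward direction holds however 12.5 is read.** It requires that any death without re-evaluation be kept. If *beforehand* meant only before a Day 28 assessment, later deaths among leavers would be dropped as well, and with 20% poor-prognosis leavers the estimate would rise (0.468 against 0.426). This is a further reason to take the condition out of the survival endpoints.
- **That EFS on all patients entered cannot be delivered**, because Section 4 says "Further data will not be collected if the patient has not begun study treatment at the time of removal from trial". Section 4 treats those registrants as screen or baseline failures and replaces them, so they can reasonably be regarded as not entered.
- **That time zero is Day 0**, because 12.6.2 speaks of assessments "at D0 (trial entry) and the end of every other month for 1 year". That sentence schedules quality-of-life and function measures, not survival.

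**Conclusion.** The point holds as a conflict between 9.2 and 12.5, with an inclusion rule in 12.5 that depends on the outcome being estimated. Read as keeping every death without re-evaluation, that rule can only lower Kaplan-Meier OS relative to all treated patients. Its size cannot be known from the documents. At n = 24 it runs from under 1 point at 6 months (leavers lost by Day 28) to about 5 points (20% followed beyond 6 months without re-evaluation, with the same survival as the rest). The upper end rests on a leaver rate and follow-up pattern that the documents do not support, and even so is about half of one standard error.

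OS and EFS are secondary endpoints with no power claimed, and neither the MTD nor the recommended phase II dose uses them. The point should be corrected because the correction is cheap and the published survival curves would otherwise rest on a set chosen after the fact. It does not threaten the trial's main conclusion.

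**What to change.** - **Section 9.2:** define OS and EFS on one set, all patients who received at least one dose of either study drug, measured from the first dose of study drug. Delete *evaluable* from the OS row. Timing from first dose fixes membership at time zero; timing from registration would not, because dosing comes up to 5 business days later (Section 4).
- **Section 12.5:** state that the condition of re-evaluation or prior death applies to response only. Patients not re-evaluated stay in OS and EFS and are censored under the existing 9.2 rules: last known alive for OS, last examined for EFS. Correct the cross-reference to 12.6.2.

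The cost is a wording amendment to two sections. Sections 4 and 7.2 already require follow-up of every treated patient, so no new data, visits or patients are needed.
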